We conducted a clinical demonstration project to gather preliminary data regarding Brief CBT-CP effectiveness and acceptability among patients and providers (12). Nationally, 22 PCMH providers across 22 primary care clinics responded to an invitation to participate in a 12-month demonstration project that included training in Brief CBT-CP. At the end of the project period, data from 118 unique patients treated with Brief CBT-CP by a participating PCMH provider were analyzed to assess changes in outcomes. Although not a randomized controlled trial (RCT), patient reported outcome data collected by the PCMH providers at each visit showed statistically significant improvement in the PEG (13) of moderate effect size by session three ($d = 0.65$). This one-point decrease in PEG scores indicated that clinically significant improvement in outcomes can potentially be made in as few as three, 30-minute appointments of Brief CBT-CP. Pain self-efficacy showed smaller but also statistically significant improvements ($d = 0.22$).

Significance and Relevance for Veterans and VA Healthcare

The long-term goal of this research is to promote recovery among Veterans with chronic musculoskeletal pain. The focus of the intervention (i.e., a CBT intervention to improve functional outcomes commonly impacted by chronic pain) directly addresses the current RR&D special emphasis area related to non-pharmacological activity-based interventions for chronic pain. Taken together, these related high priority topics reflect ORD-wide clinical priorities and the VA's current Strategic Plan (FY19-24).

Research Design and Methods

Participants.

We will recruit and randomize 184 Veterans (not including screening failures) who utilize one of the primary care clinics located at the regional VAMC and CBOCs in Western and Central New York. Eligible participants will be randomized in a 1:1 ratio into either (1) Brief CBT-CP plus primary care TAU or (2) primary care TAU only.

Eligibility and recruitment.

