modeling (MLM) using a random coefficients model will be used to test this hypothesis by assessing the group by time fixed effect coefficient. A sample size of 184 (92 per group) offers at least 80% power to detect a small to medium effect of .35 in the group by time coefficient with an experiment-wise alpha of .05 (2-tailed). To estimate sample size, we employed the method proposed by Hedeker, et al. for multilevel longitudinal designs (18) using results from our Brief CBT-CP clinical demonstration project. Our sample size is adjusted for an overall 25% attrition rate split across treatment (12%) and follow-up (13%) study periods.

Statistical Analysis

Statistical analyses will be conducted using SAS v9.4. The primary analysis will be conducted using the intention-to-treat approach; participants who are randomized will be analyzed according to their assigned group regardless of amount of treatment received. The data will be screened for missing cases, outlier scores, and non-normal response distributions. Assumptions underlying statistical models will be assessed by examining standardized residuals, influence diagnostics, and homogeneity of variance (e.g., among groups).

A multilevel model (MLM) will be used to test the primary null hypothesis of no difference in pain-related activity interference measured by the BPI Interference subscale between Brief CBT-CP plus TAU and TAU-only against the two-sided alternative. Our MLM will consist of fixed and random effects. Fixed effects will consist of group, time of assessment, and a cross-level interaction between condition and time. The condition effect compares the baseline BPI-I score between Brief CBT-CP plus TAU and TAU-only. Time will be entered in our model as a nominal variable representing effects relative to baseline at weeks. In other words, baseline (t0) will be defined as the reference level allowing dummy indicators to estimate differences in BPI-I from baseline. The β of the 12-week primary treatment effect will be tested against a two-sided alternative.

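### Does the stated 80% power for an effect of .35 fail to carry over to the 12-week coefficient that is actually tested?

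*Combined protocol and SAP*

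**What the plan says.** The Power Analyses section states that "A sample size of 184 (92 per group) offers at least 80% power to detect a small to medium effect of .35" in the group-by-time coefficient of a random coefficients model, at a two-sided alpha of .05. It adds: "Our sample size is adjusted for an overall 25% attrition rate split across treatment (12%) and follow-up (13%) study periods". It names a published method for longitudinal designs with attrition and takes its inputs from the team's demonstration project. It gives no SD, within-person correlation, variance components, number of occasions or time contrast.

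The Statistical Analysis section enters time as a nominal variable with baseline as the reference level and says: "The β of the 12-week primary treatment effect will be tested against a two-sided alternative".

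The preliminary-studies text describes the demonstration project as not randomised and reports that "data collected by the PCMH providers at each visit showed statistically significant improvement in the PEG (13) of moderate effect size by session three". It gives no BPI figures. Under Consenting and baseline assessment, entry requires a BPI interference score of at least 4. Under Procedures, a 12-week assessment is described, while payment is offered for three follow-ups.

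**The concern.** Three features together make the 80% look unreliable.

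- **Contrast.** Power is stated for a group-by-time coefficient with attrition running into a follow-up period. The primary test is one contrast, week 12 against baseline. A calculation for a trend or for an average over several follow-ups could flatter it.
- **Inputs.** They come from an uncontrolled project described in terms of the PEG at clinic visits, not BPI interference over 12 weeks.
- **Entry rule.** Cutting the baseline score at 4 narrows its range, which lowers its correlation with the week-12 score.

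If the true correlation were near .5, power for .35 would be about 60%. A null result might then be read as stronger evidence against an effect of that size than it is.

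**Working it through.** **Inputs from the documents.** 92 per arm; 1:1 allocation; two-sided .05; effect .35; loss of 12% by the end of treatment and 25% overall. Completers per arm: 92 × 0.88 = 81 at week 12, and 92 × 0.75 = 69 after all attrition.

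**Inputs assumed.** The .35 is in raw BPI interference SDs, with equal variance at both visits. The baseline-to-week-12 correlation r is not given, so it is varied.

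**Can the plan's figure be reproduced?** Not without choosing r. The between-arm difference in change has per-person SD √(2(1 − r)), so completers per arm for 80% power are

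n = 2 × (1.96 + 0.842)² × 2(1 − r) / 0.35².

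- At r = .73: 2 × 7.851 × 0.54 / 0.1225 = 69.2, and 69.2 / 0.75 = 92.3 randomised per arm. This is the stated size, from the primary contrast and the stated 25% attrition.
- At r = .5: 128.2 completers, or 128.2 / 0.88 = 146 randomised per arm at 12% loss and 128.2 / 0.75 = 171 at 25% loss.

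**Power of the change contrast** (noncentral t, standardised effect 0.35 / √(2(1 − r))):

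| r | 92 per arm (no loss) | 81 per arm (12% loss) | 69 per arm (25% loss) |
|---|---|---|---|
| .4 | 0.58 | 0.52 | 0.46 |
| .5 | 0.66 | 0.60 | 0.53 |
| .6 | 0.75 | 0.70 | 0.63 |
| .7 | 0.86 | 0.82 | 0.75 |
| r needed for 80% | .645 | .69 | .735 |

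The conditional arithmetic behind the concern is therefore right.

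**Other readings.**

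- A mixed model that keeps the baselines of dropouts (12% loss): 62% at r = .5; 80% needs r = .68.
- A linear trend over four occasions under compound symmetry, with .35 reached at the end and losses of 12%, 6.5% and 6.5%: 62% at r = .5; 80% needs r = .68.
- The average of three follow-ups against baseline, same losses and structure: 78% at r = .5; 80% needs r = .52.
- A baseline-adjusted comparison, which the plan does not specify, with SD √(1 − r²) and 81 per arm: about 0.73 at r = .5; 80% needs r = .61.
- .35 in change-score SDs: 0.60 with 81 per arm and 0.53 with 69, whatever r is.

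**Contrast.** With time nominal and baseline as reference, the coefficient for group by week 12 is a group-by-time coefficient. The Power Analyses section also places its hypothesis across the 12-week treatment period. The average of follow-ups at r near .5 comes close to 92 per arm, but so does the primary contrast at r = .73. Nothing in the documents prefers the first.

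**Entry rule.** Take a bivariate normal model with r = .70 before selection, mean 4.5 to 6 and SD 2.0 to 2.4 (all assumed), and keep baseline scores of at least 4. The correlation falls to about .53 to .61. Baseline variance also shrinks, so the SD of change falls from √(2 × 0.30) = 0.775 to about 0.74–0.75 of the unselected SD. For a fixed effect in BPI points, power with 81 per arm moves from 0.82 to about 0.84–0.85. The lower correlation cannot be put into the table above, because that formula needs equal variances at the two visits.

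**The case for a change.** The strongest case for acting is that few readings rescue the claim at moderate correlations. At r = .5 with 81 per arm, the effect detectable with 80% power is 0.44 SD as written and 0.38 SD with baseline adjustment. If .35 is in change-score SDs, no correlation brings power to 80%; even without loss it is 0.66. The source project offers no BPI correlation, and the selected sample's own SD, if that is what scales .35, would make the entry rule count against power. A short table would cost nothing.

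Much of this stands as a description of what is undisclosed. The reader cannot tell which scale or correlation was used, and the 80% is unverified. It does not stand as a demonstrated error. Each unfavourable figure needs a scale or correlation that the documents do not state, while r near .7 on the raw scale supports the claim. The 25% allowance is more than a 12-week endpoint needs, since only the 12% treatment-period loss bears directly on it. The plan also contains no rule that would treat a null result as excluding .35. Computing power for a baseline-constrained model would describe an analysis other than the one specified.

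**Conclusion.** No change to the plan follows. The 80% can be neither reproduced nor refuted, because the scale of .35 and the correlation are missing. On the raw-SD reading with 81 per arm, power runs from about 0.52 at r = .4 to 0.82 at r = .7, crossing 80% at about .69. With 69 per arm the crossing is about .735. These ranges assume equal variances and an unadjusted change contrast. The stated 92 per arm follows from the primary contrast at r = .73 with 25% loss, so the plan's figures are mutually compatible. The claim that a different contrast was powered is not shown, and the entry-rule argument fails for an effect fixed in BPI points.

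The gap is one of reporting in a planning calculation. Filling it would leave the 184 participants, the 12-week test and its result unchanged, and would correct no figure shown to be wrong. When the result is in, the confidence interval for the 12-week coefficient will show which effects are excluded, whatever correlation was assumed at the design stage.
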